#### **4.2.1 Lost to Follow-Up**

A participant will be considered lost to follow-up if he or she repeatedly fails to return for scheduled visits and is unable to be contacted by the study site.

The following actions must be taken if a participant fails to return to the clinic for a required study visit:

- The site must attempt to contact the participant and reschedule the missed visit as soon as possible and counsel the participant on the importance of maintaining the assigned visit schedule and ascertain whether the participant wishes to and/or should continue in the study.
- Before a participant is deemed lost to follow-up, the investigator or designee must make every effort to regain contact with the participant (where possible, 2 telephone calls and, if necessary, a certified letter to the participant's last known mailing address or local equivalent methods). These contact attempts should be documented in the participant's medical record.
- If the participant continues to be unreachable, he/she will be considered to have withdrawn from the study.

#### **4.2.2 Replacements**

Participants who withdraw may be replaced at the discretion of the sponsor after consultation with the SRT. Participants who are assigned to a group in error and not vaccinated may be replaced. Participants who withdraw for reasons connected to the study vaccine (eg, safety concerns after study vaccination) will not be replaced.

If the investigator believes there is a reasonable justification to do so, all screening procedures may be repeated (maximum 1 rescreening per individual is allowed). Only results from the rescreening visit, if it occurs, will be taken into consideration and recorded in the eCRF. The participant can only be vaccinated once the investigator receives the results and confirms the eligibility criteria.

## 5 Study Vaccines

### 5.1 Method of Assigning Participants to Study Vaccine Groups

Participants in Part A will be assigned sequentially to a dose-level cohort by age group ([Section 3.1](#)). Participants in Part B will be randomly assigned on Day 1 to receive study vaccine by dose-level cohort.

Interactive response technology will be used to administer the randomization schedule. Biostatistics will generate the randomization schedule using SAS software Version 9.4 or later (SAS Institute Inc, Cary, North Carolina) for IRT, which will link sequential participant randomization numbers to treatment codes. Note: If a participant is consented electronically, a participant number may be generated; however, that number will be updated to align with the IRT number after randomization is complete for consistency in each participant's study records.

### 5.2 Study Vaccine Administration

Participants will receive 1 dose of IP on Day 1, in accordance with the study's SOE ([Table 13-1](#)). The volume to be administered will vary by dose level over a potential range of 0.3 mL to 0.7 mL; full details are described in the Pharmacy Manual.

Study intervention should be administered intramuscularly into the deltoid muscle, preferably of the nondominant arm. The needle length recommendations for adults (by sex and weight) receiving an intramuscular injection in the deltoid muscle are as follows ([CDC 2022b](#)):

- Men and women, < 70 kg (152 lb): 25 mm (1 inch)
- Men, 70-118 kg (152-260 lb); Women, 70-90 kg (152-200 lb): 25-38 mm (1-1.5 inches)
- Men, > 118 kg (260 lb); Women, > 90 kg (200 lb): 38 mm (1.5 inches)

Standard vaccination practices must be observed, and vaccine must not be injected into blood vessels. Appropriate medication and other supportive measures for management of an acute hypersensitivity reaction should be available in accordance with local guidelines for standard immunization practices.

Administration of IP should be performed by an appropriately qualified, GCP-trained, and vaccine-experienced member of the study staff (eg, physician, nurse, physician's assistant, nurse practitioner, pharmacist, or medical assistant) as allowed by local, state, and institutional guidance. Details of IP administration will be recorded in the eCRF.

Refer to the Pharmacy Manual for additional instructions on study vaccine administration.

### 5.3 Identity of Investigational Product

Investigational product in this Phase 1 study refers to the CV0501 vaccine, which is a formulation of **CCI** [REDACTED] [REDACTED] that will be administered during the study.

CCI

The IP information is presented in [Table 5-1](#).

**Table 5-1** **Investigational Product Information**

Intervention Name	CV0501
Type	Vaccine
Dose Formulation	Modified mRNA
Unit Dose Strength(s)	[REDACTED] CCI µg mRNA/mL
Dosage Level(s)	3, 6, 12, 25, 50, 75, 100, 150, 200 µg
Route of Administration	Intramuscular injection
Diluent	0.9% sodium chloride
Use	Experimental
IMP or NIMP	IMP
Sourcing	Provided centrally by GSK Biologicals SA or [REDACTED] CCI

Packaging and Labeling	IP will be provided in a glass vial as a sterile colloidal dispersion in a frozen liquid formulation as open-label supply. Each vial will be labeled as required per country requirement.
-------------------------------	---

Diluent (0.9% sodium chloride solution for injection) will be provided centrally by PPD in a glass or plastic vial as open-label supply. Each vial will be labeled as required per country requirement.

Refer to the Pharmacy Manual for instructions on how to prepare and dispense the IP. Appropriately qualified and experienced study staff (eg, physician, nurse, physician's assistant, nurse practitioner, pharmacy assistant/technician, or pharmacist), as allowed by local, state, and institutional guidance, should prepare and dispense IP. A second staff member will verify the dispensing.

## **5.4 Management of Clinical Supplies**

### **5.4.1 Investigational Product Packaging and Storage**

Investigational product will be supplied in vials that will require further dilution and preparation procedures; please refer to the Pharmacy Manual for additional packaging and preparation details. The IP must be stored in a secure, restricted freezer and kept at the temperature noted in the Pharmacy Manual at each stage of preparation for IM administration.

Once prepared and diluted for IM administration, refer to the Pharmacy Manual for storage conditions. The investigator or designee must confirm appropriate temperature conditions have been maintained during transit for all IP received and any discrepancies are reported and resolved before use of the IP.

Refer to the Pharmacy Manual for further details regarding storage and preparation requirements.

### **5.4.2 Investigational Product Accountability**

The investigator will maintain accurate records of receipt of all IP, including dates of receipt. In addition, accurate records will be kept regarding when and how much IP is administered to each participant in the study. Only participants enrolled in the study may receive the IP and

only authorized site personnel may supply or administer the IP. Reasons for departure from the expected dispensing regimen must also be recorded. At the completion of the study, to satisfy regulatory requirements regarding drug accountability, all IP will be reconciled and retained or destroyed according to applicable regulations. Further guidance and information for the final disposition of unused IP are provided in the Pharmacy Manual.

### **5.4.3 Other Supplies**

Refer to the Pharmacy Manual for ancillary formulation preparation or injection materials that will be distributed by PPD to the study sites or that the study sites will need to procure.

In addition, PPD will provide the following participant supplies to study sites: eDiary devices, rulers, thermometers, and informational cards describing solicited symptoms and symptoms of COVID-19.

## **5.5 Overdose Management**

An overdose is any dose of study vaccine given to a participant that exceeds the planned dose for an individual participant within a given group.

There is no specific treatment recommended for an overdose.

Any overdose must be promptly reported to PPD within 24 hours. Overdose itself is not to be reported as an AE. However, any AEs associated with the overdose are to be reported in the relevant AE/SAE sections of the eCRF.

In the event of an overdose, the investigator should:

1. Contact the medical monitor immediately.
2. Closely monitor the participant for any AE/SAE and laboratory abnormalities for at least 3 days. Refer the participant to a higher level of care as clinically indicated.
3. Document the quantity of the excess dose in the eCRF.

Decisions regarding dose interruptions or modifications will be made by the investigator in consultation with the medical monitor based on the clinical evaluation of the participant.

## 5.6 Blinding

Allocation of participants to vaccine groups will proceed as described in [Section 5.1](#). In the event of a quality assurance audit, auditors will be allowed access to study vaccine records at the study sites to verify that dispensing was performed accurately.

In this open-label study, the study staff receiving, storing, dispensing, preparing, and administering the study interventions will be unblinded. Study and site personnel, including the investigator, study staff and participants will be unblinded.

Preliminary reviews of available safety and immunogenicity data may be performed on an ongoing basis in an unblinded fashion. A statistical and programming team will perform 2 planned interim analyses during the study ([Section 7.7](#)). Unblinded safety summaries will be provided to the SRT to inform study decisions for progressing enrollment between groups ([Section 3.1.1](#)).

## 5.7 Compliance With Study Vaccine

All participants will be vaccinated at the study site by the investigator or designee, under medical supervision. The date and time of study vaccine administration will be recorded in the source documents and in the eCRF. The dose of study vaccination and participant identification will be confirmed at the time of dosing by a member of the study site personnel other than the person administering the study vaccination.

When the individual dose for a participant is prepared from a bulk supply, the preparation of the dose will be confirmed by a second member of the study site personnel.

## 5.8 Prior, Concomitant, and Rescue Therapies

### 5.8.1 Prior and Concomitant Therapy

Use of all prior and concomitant medications and vaccinations within 6 months of screening will be recorded in the participant's eCRF.

All prior COVID-19 vaccines received (including those received more than 6 months before screening) and all COVID-19 vaccines received during the study will be recorded.

The minimum requirement is that drug name and the dates of administration are to be recorded. This will include all prescription drugs and vaccinations. In addition, any herbal products, vitamins, minerals, and over-the-counter medications taken within 2 weeks of study vaccination should also be recorded in the participant's eCRF. Any changes in concomitant medications also will be recorded in the participant's eCRF throughout the study.

### **5.8.2 Allowed Concomitant Therapy**

Any concomitant medication deemed necessary for the welfare of the participant during the study may be given at the discretion of the investigator. However, it is the responsibility of the investigator to ensure that details regarding the medication are recorded in full in the eCRF.

Participants during this Phase 1 study will be allowed to receive a booster dose of a licensed or authorized COVID-19 vaccine, per national recommendations, if received at after the Day 29 visit.

No concomitant medications will be provided by the sponsor or PPD.

### **5.8.3 Rescue Medicine**

There are no known rescue medications for the IP; supportive care should be provided to participants as clinically indicated.

## **5.9 Study Holding Rules**

The medical monitor, investigator, and SRT will continuously assess AEs against study holding rules ([Table 5-2](#)).

**Table 5-2****Study Holding Rules**

Study Holding Rule	Study Holding Rule Description	Number of Participants Needed to Trigger a Study Hold
1a	Death or any life-threatening SAE regardless of causality	≥1
1b	Any non-life-threatening SAE that cannot be reasonably attributed to a cause other than vaccination as per investigator or sponsor assessment	≥1
1c	Necrosis at the injection site	≥1
1d	Confirmed or suspect myocarditis or pericarditis events not clearly attributable to any cause other than study vaccine	≥2
2a	Any same or similar Grade 3 related unsolicited events*, including but not limited to the identical MedDRA high-level term	≥2
2b	Same Grade 3 solicited local or systemic AE in an investigational group	≥3

\* Includes laboratory abnormalities of clinical relevance, symptomatic or not, as determined by the investigator.

Study holding rules 1a, 1b, and 1c will be assessed by the investigators on a continuous basis. Study holding rules will lead to a hold of the vaccination in the entire study. Study holding rules 1d, 2a and 2b will be assessed by the SRT on an ongoing basis. A triggered study holding rule will lead to a hold of vaccination in the entire study.

If the sponsor confirms that a stopping rule has been met, the following actions will be taken:

1. The SRT ([Section 11.1](#)) will review all available safety data whenever any of the study holding rules are met. The SRT will recommend to the sponsor whether a cohort or group should be permanently stopped, modified, or continued unchanged. Medical judgment, considering all available safety data at the time of review, should be the basis for a recommendation to continue the study or not.
2. The stopping rule will pause enrollment and study intervention administration for all dose levels and age groups.
3. For all vaccinated participants, all other routine study activities, including ongoing data entry, reporting of AEs, participant reactogenicity eDiary completion, blood sample collection and participant follow-up will continue during the pause.

4. Ethical and regulatory authorities will be notified per local requirements.

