### **6.1.1.2.1 Assessment of Intensity**

The intensity, or severity, of an AE refers to the extent to which an AE affects the participant's daily activities.

Solicited AEs will be graded in intensity by the participant. The investigator will assess the maximum intensity that occurred over the duration of the event for all unsolicited AEs, including SAEs, recorded during the study. The assessment will be based on the investigator's clinical judgment.

The intensity of the following solicited events will be assessed as described in [Table 6-1](#).

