## 6.1.4 Clinical Safety Laboratory Assessments

The following laboratory assessments will be performed at the time points specified in the SOE ([Table 13-1](#)):

Hematology:	Basophils, eosinophils, erythrocytes (red blood cells), hemoglobin, leukocytes (white blood cells), lymphocytes, monocytes, neutrophils, and platelets
Chemistry:	Alanine aminotransferase, alkaline phosphatase, aspartate aminotransferase, total and direct bilirubin, blood urea nitrogen, and creatinine
SARS-CoV-2:	

• SARS-CoV-2 N protein serology (Ab) prevaccination and postvaccination to monitor for asymptomatic SARS-CoV-2 infections

• SARS-CoV-2 RT-PCR (nasopharyngeal or mid-turbinate swab)

HIV/HBV/HCV	

• Hepatitis B surface antigen test

• HIV 4th generation antigen/Ab test

• Anti-HCV Ab test (and RNA test if anti-HCV Ab positive)

Other analyses:	Female participants of childbearing potential: β-human chorionic gonadotropin (serum test at screening; urine test at additional time points) Serum FSH, to confirm postmenopausal status per Appendix 13.2

The clinical safety laboratory assessments will be performed by a local or central laboratory as detailed in the Laboratory Manual. Screening laboratory tests may be repeated once for enrollment requirements.

The investigator must review the laboratory reports, document this review, and record any clinically relevant changes occurring during the study. If the laboratory reports are not

transferred electronically, the values must be filed with the source information (including reference ranges). Any clinically relevant laboratory results should be reported as an AE or SAE and graded with the AE intensity grading scale ([Section 6.1.1.2.1](#)).

All laboratory tests with values considered clinically significantly and abnormal during participation in the study should be evaluated for the etiology and should be repeated until the values return to normal or baseline or are no longer considered clinically significant by the investigator or medical monitor. If such values do not return to normal/baseline within a period of time judged reasonable by the investigator, the sponsor should be notified.

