9.2 Clinical Laboratory Evaluations

The following laboratory assessments will be performed:

Hematology:	Basophils, eosinophils, erythrocytes (red blood cells), hemoglobin, leukocytes (white blood cells), lymphocytes, monocytes, neutrophils, and platelets
Chemistry:	Alanine aminotransferase, alkaline phosphatase, aspartate aminotransferase, total and direct bilirubin, blood urea nitrogen, and creatinine
SARS-CoV-2:	
 SARS-CoV-2 serology (antibody) will include N protein for prevaccination and postvaccination timepoints. SARS-CoV-2 RT-PCR (nasopharyngeal or mid-turbinate swab)
HIV/HBV/HCV	
 Hepatitis B surface antigen test HIV 4th generation antigen/Ab test Anti-HCV Ab test (and RNA test if anti-HCV Ab positive)
Other analyses:	
Female participants of childbearing potential:
 
 β-human chorionic gonadotropin (serum test at screening; urine test at additional time points) Serum FSH, to confirm postmenopausal status

Individual safety laboratory measurements for hematology, chemistry and coagulation laboratory panel will be provided. All listings will include the cohort, study vaccine, participants ID, laboratory test name result, date and time of measurements, reference range, and flag for measurements that are outside the reference range and sorted by age group, dose group and participant number.

Laboratory abnormalities will be graded for severity using the FDA toxicity grading table (DHHS 2007). Clinically relevant laboratory abnormalities will be reported as AEs using the AE grading.

A summary of patients with an abnormal laboratory value after study vacation (up to Day 8) will be presented. An abnormal laboratory is defined as any value outside of the normal range.

A by-participant listing will be provided for pregnancy test by age group, dose group and participant number.

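### Holding rule 2a counts Grade 3 laboratory abnormalities without naming a grading scale, and the two scales in the plan would ordinarily disagree for symptomless values

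*Protocol*

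**What the plan says.** **The rule.** Rule 2a in Protocol Table 5-2 covers "Any same or similar Grade 3 related unsolicited events" and is triggered by two or more participants. The footnote extends it to laboratory findings: "Includes laboratory abnormalities of clinical relevance, symptomatic or not, as determined by the investigator". Neither the rule nor the footnote says how such a finding is graded. On who applies the rule, Protocol 5.9 states: "Study holding rules 1d, 2a and 2b will be assessed by the SRT on an ongoing basis".

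**Scale A, functional.** Protocol 6.1.4 says: "Any clinically relevant laboratory results should be reported as an AE or SAE and graded with the AE intensity grading scale". That scale is in 6.1.1.2.1. Grade 1 is easily tolerated and leaves daily life undisturbed. Grade 3 stops the participant from carrying on daily life. For unsolicited AEs, "The assessment will be based on the investigator's clinical judgment".

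**Scale B, numeric.** Protocol 7.5.2 and Appendix 13.5 grade laboratory abnormalities by the FDA table (Table 13-4). Appendix 13.5 adds that clinically relevant abnormalities of Grades 1 to 3 are reported as AEs and that Grade 4 values are reported as SAEs.

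**SAP 9.2** has both. One sentence reads "Laboratory abnormalities will be graded for severity using the FDA toxicity grading table"; the next reads "Clinically relevant laboratory abnormalities will be reported as AEs using the AE grading".

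**The pointer.** Protocol 6.1.1.2.1 sends the reader to Section 6.1.2 for the grading of laboratory AEs. Section 6.1.2 deals with SARS-CoV-2 infection and COVID-19 and contains no laboratory grading.

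**The concern.** The footnote plainly wants symptomless laboratory findings to count. The grading instruction that sites are given in 6.1.4 works against this, because on a scale defined by interference with daily life a symptomless value would ordinarily be graded below 3.

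This is a first-in-human dose escalation planned up to 200 µg. Scheduled hematology and chemistry after vaccination are drawn at Day 8, so the plan is set up to find abnormalities that cause no symptoms. If sites enter such values at a low intensity grade and the SRT counts grades as entered, the rule 2a count could miss them. The gap is mainly at Table 13-4 Grade 3. Grade 4 values are SAEs and can reach rules 1a or 1b at a single participant.

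**Working it through.** **Step 1: the same result on both scales.** Take a symptomless ALT of 6 x ULN, assessed by the investigator as related and clinically relevant.

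| Scale | Source | Grade 3 means | Result | Counts toward 2a? |
|---|---|---|---|---|
| Numeric | Protocol 7.5.2, 13.5, Table 13-4 | ALT 5.1 to 10 x ULN | Grade 3 | Yes |
| Functional | Protocol 6.1.4, via 6.1.1.2.1 | Stops daily activities | Ordinarily Grade 1 | Ordinarily no |

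Two such participants trigger a study-wide hold on the first scale and ordinarily do not on the second. ALT is only an example: all 17 rows of Table 13-4 (10 hematology, 7 chemistry) define Grade 3 by a numeric limit, with no condition on symptoms.

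**Step 2: does another passage assign the scale?** Table 5-2 and its footnote do not. SAP 9.2 gives both scales and concerns reporting, not the hold. The pointer in 6.1.1.2.1 leads to a section without laboratory grading. Appendix 13.5 links the numeric Grades 1 to 3 to AE reporting, which favors Table 13-4, whereas 6.1.4 favors the intensity scale.

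**Step 3: how often could it matter?** The plan states no figure to reproduce and gives no rate for such events, so this is an illustration.

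- Number at risk: n = 30 per cohort x 5 cohorts = 150 (Part A, Protocol Table 3-1). All of Part A is used because rule 2b is limited to one group ("Same Grade 3 solicited local or systemic AE in an investigational group") and rule 2a is not.
- Assumed rate p of one kind of related, clinically relevant abnormality at Table 13-4 Grade 3, constant over dose (a simplification).
- Chance that two or more participants have it: P = 1 − (1−p)^n − n·p·(1−p)^(n−1).

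For p = 1%: 1 − 0.99^150 − 1.5 x 0.99^149 = 1 − 0.2215 − 0.3355 = 0.443.

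| Assumed p | P(rule 2a met), all cases graded by Table 13-4 |
|---|---|
| 0.1% | 1.0% |
| 0.5% | 17.3% |
| 1% | 44.3% |
| 2% | 80.4% |

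If only a share f of these cases is entered as Grade 3, p is replaced by f·p. With f = 50% (also an assumption), a true rate of 1% behaves like 0.5%, and the chance falls from 44.3% to 17.3%. At a true rate of 0.1% there is little to lose, because the rule is rarely met on either scale.

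**The case against.** The best reply is that the plan does assign a scale. Rule 2a counts unsolicited events, the investigator grades the intensity of all unsolicited AEs, and 6.1.4 and SAP 9.2 put laboratory AEs on the intensity scale. Table 13-4 would then be a separate layer for laboratory summaries. If the 6.1.1.2.1 pointer is a numbering slip for 6.1.4, it too ends at the intensity scale, which is fully defined there. This is a coherent reading. But it leaves the footnote's inclusion of symptomless abnormalities with little force, and it does not account for 13.5 tying the numeric grades to AE reports. A stated grading instruction would still undercut a stated safety hold.

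Several parts of the reply stand:

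- A reader might infer that a symptomless value can never be Grade 3 on the intensity scale. The documents do not support that. Grading rests on clinical judgment, and the Grade 3 example mentions corrective therapy. The defensible word is ordinarily.
- A reader might infer a known probability of a missed hold. None can be derived, since both the rate and the share entered as Grade 3 are assumptions.
- A reader might infer that the laboratory endpoint is affected. It is not: SAP 9.2 defines an abnormal result there as any value outside the normal range.
- There are real safeguards. The SRT assesses rule 2a itself, reviews Day 8 safety data from at least 10 participants before each Part A dose escalation, and can stop enrollment at a dose. Abnormal results are to be recorded as AEs (Protocol 6.1). These reduce the risk, but a discretionary review is not the prespecified study-wide hold.

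**Conclusion.** The point holds as an inconsistency that should be fixed. Rule 2a lacks a grading scale for laboratory abnormalities, and the two scales in the plan would ordinarily give different grades to the same symptomless value. The consequence is a hold that could be missed or delayed, mainly for Table 13-4 Grade 3 values. That conclusion rests on the text alone, and on sites applying 6.1.4 as written.

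The size is not known. Across assumed rates of 0.1% to 2% in 150 participants, full Table 13-4 grading meets the rule between about 1% and 80% of the time. How much of that would be lost depends on how literally sites use the intensity scale. A further effect is on reporting: the grade entered for a laboratory AE would feed the Grade 3 unsolicited AE table in SAP 9.1.5.

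**What to change.** 1. Add to the rule 2a footnote: laboratory abnormalities are graded by Table 13-4; analytes without a Table 13-4 row are graded by the AE intensity scale (Section 6.1.1.2.1). The fallback is needed because Protocol 6.1.4 also measures basophils, erythrocytes, monocytes and direct bilirubin, which have no row of their own. Naming Table 13-4 by itself would leave these ungraded for the rule.
2. Align Protocol 6.1.4 and the last grading sentence of SAP 9.2 with this, so that laboratory results reported as AEs carry the same grade. The eCRF severity field offers mild, moderate and severe only (SAP 9.1.2), so enter Grade 4 as severe and report it as an SAE, as 13.5 already requires.
3. Correct the pointer in Protocol 6.1.1.2.1 from Section 6.1.2 to Section 13.5.

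The cost is a few sentences and one cross-reference, with no added visits, samples or data. The downside is possibly more study-wide holds, limited to events that the investigator considers both related and clinically relevant. How many more cannot be stated, for the same reason that the size of the problem cannot.
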